11.1.4.1 Severity of Adverse Events

All AEs or SAEs will be assessed for severity, according to the toxicity grading scales in the US Food and Drug Administration guidance document entitled “Toxicity Grading Scale for Healthy Adult and Adolescent Volunteers Enrolled in Preventive Vaccine Clinical Trials.”

For AEs not included in the protocol-defined grading system, the following guidelines will be used to describe severity.

Mild (Grade 1): Events that are usually transient and may require only minimal or no treatment or therapeutic intervention and generally do not interfere with the subject’s usual activities of daily living.

Moderate (Grade 2): Events that are usually alleviated with additional therapeutic intervention. The event interferes with usual activities of daily living, causing discomfort but poses no significant or permanent risk of harm to the research subject.

Severe (Grade 3): Events interrupt usual activities of daily living, or significantly affects clinical status, or may require intensive therapeutic intervention. Severe events are usually incapacitating.

AEs characterized as intermittent require documentation of onset and duration of each episode. The start and stop date of each reported AE will be recorded on the appropriate DCF. Changes in the severity of an AE will be documented to allow an assessment of the duration of the event at each level of intensity.

All SAEs will be reviewed and evaluated by the protocol study team and Gritstone, and will be sent to the EC, if required.

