12.4.2 Analysis of the Primary Endpoint(s)

Summaries and analysis of safety data will be presented for the Safety Analysis Population.

Solicited reactogenicity signs and symptoms (local and systemic) will be summarized by severity for each day post GRT-R910 vaccination (Days 1-8) and as the maximum severity over all 7 days. Additionally, solicited AEs will be analyzed by taking the most severe response over the follow-up period, dichotomizing into a binary variable (none versus mild, moderate, or severe) and using standard techniques, such as exact confidence intervals (CI), to summarize the proportion of subjects reporting each symptom, any application site symptom, and any systemic symptom.

Unsolicited non-serious AEs will be collected from the time of GRT-R910 vaccination through 28 days after GRT-R910 vaccination. Unsolicited AEs will be coded by MedDRA for preferred term and system organ class (SOC). All SAEs will be collected from the time of GRT-R910 vaccination through the end of the study. SAEs will be described by detailed listings showing the event description, MedDRA preferred term and SOC, relevant dates (vaccinations and AEs), severity, relatedness, and outcome for each event. Non-serious unsolicited AEs will be summarized as number and percentage of subjects reporting at least 1 event in each MedDRA preferred term and SOC, cross tabulated by severity and relationship to study product. Additionally, the proportion of subjects and exact 95% CIs of AEs in aggregate and by MedDRA categories will be computed.

Clinical laboratory data will be summarized as change from baseline and by severity for each visit, and as the maximum over all post-vaccination visits.

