The number and percentage (with 95% Clopper-Pearson CIs [6]) of participants who reported any solicited AE on the vaccination day and through the 7 subsequent days (see the exact windows for each cohort in [Table 5](#)) will be tabulated by grade and treatment group for each vaccination. Percentages will be based upon the number of participants in the Safety Analysis Set within each vaccination group. Subjects will be counted once for the most severe event in cases where the subject reported more than one event per solicited AE category (e.g., injection site pain). In addition, the duration (in days) of solicited AEs after each vaccination will be summarized by treatment group for each vaccination. Duration will be calculated as the number of days of the Solicited AE during the special window ([Table 5](#)).

Table 5 Windows for solicited AEs per Cohort

Cohort	Vaccination Day	Windows for Solicited AEs
1 and 2 (Subjects NOT RECEIVING booster dose)	Day 1	Day 1 through Day 8
1 and 2 (Subjects RECEIVING booster dose)	Day 1	Day 1 through Day 8
	Day 113	Day 113 through Day 120
3, 4, and 6	Day 1	Day 1 through Day 8
	Day 29	Day 29 through Day 36

All solicited local and systemic AEs will be presented in the data listings, including a listing of solicited AEs.

Calculation of Solicited AEs duration

The number of days will be calculated at the level of subject, vaccination (prime or booster), and symptom as the longest duration of consecutive days after the injection (including the day of injection) the subjects' reported solicited AE occurs with a toxicity grade > 0. If the solicited AE continues beyond 8 days, the days from the solicited AE reported after 8 days will be included (e.g., an event that lasted 5 days in the first 8 days post injection and 4 days beyond 8 days post injection, the duration will be reported as >8 days). A separate example below illustrates how solicited AE duration is calculated:

Subject ID	Prime/Booster	Symptom	Timepoint	Severity	Grade
G0910000999	DOSE 1	Headache	Day 1	MILD	1
G0910000999	DOSE 1	Headache	Day 2	MILD	1
G0910000999	DOSE 1	Headache	Day 3	NONE	0
G0910000999	DOSE 1	Headache	Day 4	NONE	0
G0910000999	DOSE 1	Headache	Day 5	MILD	1

G0910000999	DOSE 1	Headache	Day 6	MODERATE	2
G0910000999	DOSE 1	Headache	Day 7	MODERATE	2
G0910000999	DOSE 1	Headache	Day 8	MILD	1
G0910000999	DOSE 1	Headache	Day 9	MILD	1
G0910000999	DOSE 1	Headache	Day 10	NONE	0

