In the above example, the duration of the headache for the subject at dose 1 (prime dose) is 5 days. Note that there are two solicited AE episodes reported:

1. Starting Day 1 and ending Day 2 (2 days)
2. Starting Day 5 and ending Day 9 (5 days)

Only the length of the longest duration (the second episode) is considered, while the first episode is not. Each duration of episode is calculated via the formula:

$$\text{Duration}(days) = (\text{end date of Solicited AE recorded in Memory Aid}) - (\text{start date of Solicited AE recorded in Memory Aid}) + 1$$

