9.6. Electrocardiogram

Electrocardiogram (ECG) will be performed for Cohort 1 and 2 receiving booster dose only and Cohort 3, 4, and 6.

The ECG data will include heart rate and RR, PR, QT, and QRS durations. The investigator will be responsible for providing the interpretation of clinical significance for all ECG results.

The ECG assessments will be summarized as mean, SD, median, min, max, and mean of actual value and as mean, SD, median, min, and max of change from baseline. An interpretation by study days table in ECG will be summarized for the SAF

For subject with Early Termination (ET) visit, the ET visit will be set to the next protocol scheduled visit following ET within the specific study period. If the subjects completed all the scheduled visits and then discontinued, no mapping will be done.

All the ECG data will be listed.

10. Interim Analysis

No interim analysis was planned for this study; however, there may be unplanned interim analyses in light of the nature of Phase 1 study.

11. Changes in the Planned Analysis

- Efficacy analysis was added to the section 8.1
- Explained the occurrence of potential unplanned interim analyses in section 10.
- Calculation of solicited AE duration in section 9.1.2

12. References

1. ICH. Guidance for Industry (E9 Statistical Principles for Clinical Trials)
2. Gritstone bio, Inc. Clinical study protocol GO-009 Version 5.0 09 Feb 2023.
3. https://www.sas.com/en_us/home.html
4. Martin Bland Prof. of Health Statistics University of York, Detecting a single event

Gritstone bio, Inc.
GO-009

Statistical Analysis Plan, Version 5.0
Date Issued: 09UN2023

5. ICH. Guidance for Industry (Integrated Addendum to ICH E6(R1): Guideline for Good Clinical Practice E6(R2))
6. Clopper, C.J., and Pearson, E.S. (1934), "The Use of Confidence or Fiducial Limits Illustrated in the Case of the Binomial", *Biometrika* 26, 404-413
7. U.S. Department of Health and Human Services Food and Drug Administration Center for Biologics Evaluation and Research, "Toxicity Grading Scale for Healthy Adult and Adolescent Volunteers Enrolled in Preventive Vaccine Clinical Trials", 2007

Approved

Gritstone bio, Inc.
GO-009

Statistical Analysis Plan, Version 5.0
Date Issued: 09JUN2023

13. Appendices

Appendix 1

Table 6 Schedule of Study Procedures: Cohorts 1 and 2 – Subjects NOT receiving booster dose

Study Visit	V00	V01	V02	V03	V04	V05	V06	V07	V08	Unsch Visit	Early Term Visit

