- 15 In case of second dose delay (± 3), all safety visits (Visit 07 to Visit 12) will be scheduled based on the day of the second dose (e.g., Visit 07 will occur 1 day after delayed second dose and not on Day 30). All visits will shift based on the second dose without changing the time interval between 2 consecutive visits.
- 16 Cohorts 3 and 4 will complete Visit 13 (Day 394) if the visit window occurs prior to the last study participant completing Visit 12 (Day 209). Cohort 6 will not complete Visit 13 (Day 394).

Approved

Gritstone bio, Inc.
GO-009

Statistical Analysis Plan, Version 5.0
Date Issued: 09JUN2023

Appendix 2

Table 9 Planned Tables, Listings, and Figures (TLFs)

#	Type	Output #	Output Header	Population
1	Table	14.1.1.1	Subject Screening and Enrollment	All Screened Subjects Analysis Set
2	Table	14.1.1.2	Subjects Disposition and Analysis Sets	Intent-to-Treat Analysis Set*
3	Table	14.1.2.2	Major Protocol Deviations	Safety Analysis Set
4	Table	14.1.3	Demographics	Safety Analysis Set
5	Table	14.1.4	Medical History	Safety Analysis Set
6	Table	14.2.1	Analysis of Incidence Rate of COVID-19 Positive Tests	Safety Analysis Set
7	Table	14.3.1.1.1	Summary of Subjects with Solicited Adverse Events Within 8 Days After the Injection of Prime Dose by Maximum Grade	Safety Analysis Set
8	Table	14.3.1.1.2	Summary of Subjects with Solicited Adverse Events Within 8 Days After the Injection of Booster Dose by Maximum Grade	Safety Analysis Set
9	Table	14.3.1.2.1	Summary of Subjects with Solicited Adverse Events Within 8 Days After the Injection of Prime Dose by Maximum Grade and Onset Day	Safety Analysis Set
10	Table	14.3.1.2.2	Summary of Subjects with Solicited Adverse Events Within 8 Days After the Injection of Booster Dose by Maximum Grade and Onset Day	Safety Analysis Set
11	Table	14.3.1.3.1	Summary of Subjects with Solicited Adverse Events Within 8 Days After the Injection of Prime Dose by Onset Day	Safety Analysis Set
12	Table	14.3.1.3.2	Summary of Subjects with Solicited Adverse Events Within 8 Days After the Injection of Booster Dose by Onset Day	Safety Analysis Set

Gritstone bio, Inc.
GO-009Statistical Analysis Plan, Version 5.0
Date Issued: 09JUN2023

13	Table	14.3.1.4.1	Subject Incidence of Solicited Adverse Events by Term Related to the Injection of Prime Dose	Safety Analysis Set
14	Table	14.3.1.4.2	Subject Incidence of Solicited Adverse Events by Term Related to the Injection of Booster Dose	Safety Analysis Set

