15	Table	14.3.1.4.3	Summary of Duration (Days) of Solicited Adverse Events Related to the Injection of Prime Dose	Safety Analysis Set
16	Table	14.3.1.4.4	Summary of Duration (Days) of Solicited Adverse Events Related to the Injection of Booster Dose	Safety Analysis Set
17	Table	14.3.1.5.1	Summary of Subjects with Solicited Adverse Events Beyond 8 Days Related to the Injection of Prime Dose by Maximum Grade	Safety Analysis Set
18	Table	14.3.1.5.2	Summary of Subjects with Solicited Adverse Events Beyond 8 Days Related to the Injection of Booster Dose by Maximum Grade	Safety Analysis Set
19	Table	14.3.1.6.1	Summary of Unsolicited TEAEs Throughout the Study	Safety Analysis Set
20	Table	14.3.1.7.1	Subject Incidence of Unsolicited TEAEs by Maximum Severity, System Organ Class and Preferred Term up to 28 Days After the Injection of Prime Dose	Safety Analysis Set
21	Table	14.3.1.7.2	Subject Incidence of Unsolicited TEAEs by Maximum Severity, System Organ Class and Preferred Term up to 28 Days After the Injection of Booster Dose	Safety Analysis Set
22	Table	14.3.1.8.1	Subject Incidence of Unsolicited TEAEs by System Organ Class and Preferred Term up to 28 Days After the Injection of Prime Dose	Safety Analysis Set

Gritstone bio, Inc.
GO-009Statistical Analysis Plan, Version 5.0
Date Issued: 09JUN2023

23	Table	14.3.1.8.2	Subject Incidence of Unsolicited TEAEs by System Organ Class and Preferred Term up to 28 Days After the Injection of Booster Dose	Safety Analysis Set
24	Table	14.3.1.9.1	Subject Incidence of Unsolicited Treatment-Related TEAEs by System Organ Class and Preferred Term up to 28 Days After the Injection of Prime Dose	Safety Analysis Set
25	Table	14.3.1.9.2	Subject Incidence of Unsolicited Treatment-Related TEAEs by System Organ Class and Preferred Term up to 28 Days After the Injection of Booster Dose	Safety Analysis Set
26	Table	14.3.1.10	Subject Incidence of Unsolicited TEAEs by System Organ Class and Preferred Term Throughout the Study	Safety Analysis Set
27	Table	14.3.1.11	Subject Incidence of Unsolicited Treatment-Related TEAEs by System Organ Class and Preferred Term Throughout the Study	Safety Analysis Set
28	Table	14.3.1.12	Subject Incidence of Serious TEAEs by System Organ Class and Preferred Term Throughout the Study	Safety Analysis Set
29	Table	14.3.1.13	Subject Incidence of Serious Treatment-Related TEAEs by System Organ Class and Preferred Term Throughout the Study	Safety Analysis Set

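### The SAP drops the protocol's day-by-day severity summary of solicited reactions and does not list this as a change, so the planned tables do not show how long reactions stayed severe

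*SAP*

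**What the plan says.** Protocol 12.4.2 specifies two summaries of solicited local and systemic reactions. They are to be "summarized by severity for each day post GRT-R910 vaccination (Days 1-8) and as the maximum severity over all 7 days".

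SAP 9.1.2 carries forward the second of these. Solicited reactions are tabulated by grade, treatment group and vaccination, and "Subjects will be counted once for the most severe event" within each solicited category. The SAP adds a duration for each subject, dose and symptom: the longest unbroken run of days on which the "reported solicited AE occurs with a toxicity grade > 0". If a symptom comes and goes, one episode counts. In the SAP's worked example, "Only the length of the longest duration (the second episode) is considered".

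The planned outputs are in SAP Appendix 2, Table 9. Items 7-18 are the solicited-reaction tables, one for each dose. The closest to a daily summary is titled "Summary of Subjects with Solicited Adverse Events Within 8 Days After the Injection of Prime Dose by Maximum Grade and Onset Day". The duration table is titled "Summary of Duration (Days) of Solicited Adverse Events Related to the Injection of Prime Dose".

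SAP section 11 lists three changes to the planned analysis: the added efficacy analysis, possible unplanned interim analyses, and "Calculation of solicited AE duration in section 9.1.2". The daily severity summary is not among them, and the SAP revision history does not mention it either.

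**The concern.** Solicited local and systemic reactions are the first two primary endpoints. Protocol 6.1 says that reactogenicity after the first dose will help to select the dose for future studies. The trial tests no hypothesis and has 10 subjects per cohort, so the descriptive tables are its result.

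One day at Grade 3 and most of a week at Grade 3 are different tolerability findings. A maximum grade beside an any-grade duration does not show which occurred. A reader may even take the two together to mean that the reaction was severe for the whole duration. The protocol's daily summary would have shown how severity rose and fell over the week. The SAP leaves it out without saying so, although section 11 does record another change to the solicited-reaction analysis.

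**Working it through.** **1. Protocol and SAP side by side**

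| Summary | Protocol 12.4.2 | SAP 9.1.2 and Table 9 |
|---|---|---|
| Severity on each of Days 1-8 | yes | no table |
| Maximum severity | yes | items 7-8; with onset day, items 9-10 |
| Onset day | not mentioned | items 11-12 |
| Incidence by term | yes | items 13-14 |
| Longest run at any grade above 0 | not mentioned | items 15-16 |
| Events beyond 8 days | not mentioned | items 17-18 |

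Onset day says when an event began, not its grade on later days, so items 9-12 do not replace the daily summary. Vital-sign toxicity grades (SAP 9.3) come from scheduled visits, so they do not supply daily fever severity.

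**2. The SAP's own example**

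Headache grades on Days 1-10 are 1,1,0,0,1,2,2,1,1,0.
- Maximum grade = 2.
- Runs above 0: Days 1-2 (2 days) and Days 5-9 (9 − 5 + 1 = 5 days). The longest is 5 days, which matches the SAP.
- Days at Grade 2: Days 6 and 7, so 2 days.

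The subject is tabulated as Grade 2 with a 5-day duration, although Grade 2 lasted 2 days.

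**3. Two constructed profiles, Days 1-8**

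| Daily grades | Maximum | First onset | Longest run above 0 | Days at Grade 3 |
|---|---|---|---|---|
| 0,3,1,1,1,1,1,0 | 3 | Day 2 | Days 2-7 = 6 | 1 |
| 0,3,3,3,3,3,3,0 | 3 | Day 2 | Days 2-7 = 6 | 6 |

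The tabulated entries are the same. With Day 2 at Grade 3, Days 3-7 at any of Grades 1-3, and Days 1 and 8 at 0, there are 3^5 = 243 such patterns. Their longest Grade 3 run goes from 1 to 6 days.

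**4. How general this is**

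All 4^8 = 65,536 eight-day profiles with grades 0-3 were enumerated, and those with maximum Grade 3 were grouped by first onset day and longest run. There are 8 + 7 + … + 1 = 36 such groups. In 34 of them, more than one count of Grade 3 days is possible. The exceptions are 1-day events starting on Day 7 or Day 8. This counts possible patterns and says nothing about how likely each one is.

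**5. What the daily summary would add**

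Assume that 3 of 10 subjects in a cohort follow one profile from step 3, the other 7 have no reaction, and no day is missing.
- Maximum Grade 3: 3/10 under either profile.
- Grade 3 on Day 4: 0/10 under the first profile, 3/10 under the second.
- Grade 3 counts summed over days, divided by the 3 affected subjects: 3/3 = 1 day each, against 18/3 = 6 days each.

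**6. What it would not add**

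Daily counts do not link days within a subject. Take two affected subjects in a cohort.
- Case A: 0,3,3,1,1,0,0,0 and 0,1,1,3,3,0,0,0.
- Case B: 0,3,3,3,1,0,0,0 and 0,1,1,1,3,0,0,0.

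In both cases each of Days 2-5 has one subject at Grade 3 and one at Grade 1. All four subjects have maximum Grade 3, onset Day 2 and duration 4 days. Yet the Grade 3 runs are 2 and 2 days in A, and 3 and 1 in B. A row for Grade 3 or higher on 2 or more consecutive days would show 2 subjects in A and 1 in B. In step 5, that row would show 0/10 (Clopper-Pearson 95% interval 0 to 31%) against 3/10 (7 to 65%).

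**The case against.** The strongest reply is that nothing is lost. Daily grades are collected on the memory aid, SAP 9.1.2 sends all solicited reactions to listings (items 98-99 of Table 9), and 10 subjects per cohort can be read line by line. This largely stands. The gap is in the summary tables, and the listings may let a reader recover the daily grades. It does not remove the mismatch, because the protocol promised a summary.

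A second reply is that the tables are being judged by their titles. No shells are shown, the SAP does not define onset day for a symptom with several episodes, and the end of Table 9 is not in the public text. This stands as a limit. A daily figure cannot be ruled out, though SAP 9.1.2 describes none. All the tables are visible, because items 1-87 are tables and the listings start at item 88.

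A third reply is that little turns on it: the 10 mcg dose was already chosen for Cohorts 3, 4 and 6, and the 6-day Grade 3 profile is a constructed extreme. That is fair, and it limits the weight of the point.

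A reader might go further in two ways that the documents do not support:
- That the omission alone is why the tables cannot separate one severe day from several. Step 6 shows that the protocol's daily counts would not always do so within a subject either. They show severity day by day in the cohort and, when no day is missing, the average number of severe days per affected subject.
- That Protocol 11.1.4.1 requires a table of duration by grade, because it has severity changes documented "to allow an assessment of the duration of the event at each level of intensity". That sentence instructs sites what to record. It does not commit the analysis to a table.

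**Conclusion.** The point holds as an undeclared departure from the protocol. One of the two severity summaries specified for the first two primary endpoints is absent from SAP 9.1.2 and from items 7-18 of Table 9, and SAP section 11 does not say so. The visible tables therefore do not show how long reactions stayed severe. A subject tabulated at maximum Grade 3, onset Day 2 and duration 6 days could have had anything from 1 to 6 days at Grade 3.

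This rests on three assumptions: table titles describe table contents, onset means first onset, and the missing pages hold no daily summary. The 3-of-10 illustration is assumed, since the documents give no such rates and expect mild to moderate reactions.

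The point is modest. It does not bias any estimate or put data out of reach. It is worth correcting because the summary was promised, bears on the tolerability result and is cheap to restore.

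**What to change.** In SAP 9.1.2 and Appendix 2, Table 9, add one table after prime and one after booster. Each should give every solicited term by grade for each of Days 1-8, by cohort, with the number missing on each day. Count the days from each injection, because the booster in Cohorts 1 and 2 may fall from 3 days before to 21 days after Day 113.

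Optionally, add one row per term for subjects at Grade 3 or higher on 2 or more consecutive days, with the Clopper-Pearson interval that SAP 9.1.2 already uses. Neither document asks for this row. It supplies the link between days that daily counts lack.

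If the sponsor prefers not to add the daily tables, section 11 should record the omission and the reason.

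The cost is two more tables, programmed from memory-aid grades already collected. No new data, visits or protocol amendment are needed.

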The reactogenicity and immunogenicity data assessed after the first dose of GRT-R910 will inform selection of the GRT-R910 dose to be tested in future studies. The 10 mcg dose of GRT-R910 was selected for use in Cohorts 3, 4, and 6 by evaluating the balance of immunogenicity and reactogenicity of a single dose of GRT-R910 in Cohorts 1 and 2.

This study will enroll 50 volunteers as follows:

- Cohort 1 (N=10, including 2 sentinels): 10 mcg GRT-R910 (after AstraZeneca) 2 doses, homologous prime-boost, booster dose will be 113 days (16 weeks) after the prime for healthy adults ≥ 60 years of age.
- Cohort 2 (N=10, including 2 sentinels): 30 mcg GRT-R910 (after AstraZeneca) 2 doses, homologous prime-boost, booster dose will be 113 days (16 weeks) after the prime for healthy adults ≥ 60 years of age.
- Cohort 3 (N=10): 10 mcg GRT-R910 (dose selected from Cohorts 1 and 2) after adenovirus based vector vaccine, homologous prime-boost, booster dose will be 28 days after the prime for healthy adults ≥ 60 years of age.
- Cohort 4 (N=10): 10 mcg GRT-R910 (dose selected from Cohorts 1 and 2) after messenger ribonucleic acid (mRNA) vaccine, homologous prime-boost, booster dose will be 28 days after the prime for healthy adults ≥ 60 years of age.
- Cohort 6 (N=10): 10 mcg GRT-R910 after messenger ribonucleic acid (mRNA) vaccine (dose selected from Cohorts 1 and 2), homologous prime-boost, booster dose will be 28 days after the prime for healthy adults ≥ 18 to ≤ 59 years of age.

[figure not shown]
Follow-up duration after the Prime dose

- For Cohorts 1 and 2 (NOT receiving booster dose): 12 months
- For Cohorts 1 and 2 (receiving booster dose): 16 months
- For Cohorts 3, and 4: up to 13 months
- For Cohort 6: 7 months

End of Study Definition

All subjects will be followed up to 12 months after the boost vaccination or prime dose for subjects not consenting to booster vaccination. Vaccinated subjects will be carefully monitored for exposure and infection to SARS-CoV-2 throughout the study.

The schedule of events is provided in [Table 6](#), [Table 7](#), and [Table 8 \(Appendix 1\)](#).

Figure 1 Study Flow Chart**3.2. Treatments**

The following dosing and administration rules will be applied to this study ([Table 1](#)):

Table 1 Dosing and Administration

Cohort	N	GRT-R910 Prime Day 1	GRT-R910 Boost 113 days (16 weeks [-3d/+21d]) after prime
1 ^a	10 ^b	10 mcg	10 mcg
2 ^a	10 ^b	30 mcg	30 mcg
	N	GRT-R910 Prime Day 1	GRT-R910 Boost 28 days after prime

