4.2. Key definitions and principles

The following principles and definitions will be applied to all tables, listings, and figures (TLFs), unless otherwise specified, are described in [Table 2](#).

Table 2 Principles and definitions for all tables, listings, and figures

Principle/definition	Value
Baseline	
Is defined as the last available valid, non-missing observation for each subject on or before the vaccination of the prime dose at V01/Day 1. Repeat and unscheduled assessments will be included in the derivation of the baseline values.

Change from Baseline	
Is defined as difference between the results collected/derived at a post-baseline visit and baseline value.
 
The change from baseline value at each post-baseline visit will be calculated for continuous parameters using the following formula:
 $\text{Change from baseline} = (\text{Result at post-baseline visit}) - (\text{Baseline value})$ 
The change from baseline value will only be calculated if the specific post-baseline visit/time point result and the baseline value for the parameter are both available and will be treated as missing otherwise. In the data listings, the change values will be set to 'N/A' (not applicable) for pre-baseline assessments.

Study Day	
Is defined as the relative day of the event starting with the date of vaccination of the prime dose (the reference day) as Day 1 (there will be no Day 0).
 
The study day of events occurring before the vaccination of the prime dose will be calculated in the following way:
 $\text{Study day (before vaccination)} = (\text{Date of event}) - (\text{Date of Vaccination of Prime Dose})$ 
For events occurring on or after the vaccination will be calculated as:
 $\text{Study day (after vaccination)} = (\text{Date of event}) - (\text{Date of Vaccination of Prime Dose}) + 1$ 
Study days will only be calculated for events with complete dates and will be undefined for events that are 'Ongoing' at the end of the study.

Display Convention of Results	
Results will be center-aligned in all summary tables and left-aligned in all listings. Subject identifiers, visits, parameter labels, and comments may be left-aligned if required.

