Review Memory Aid			X	X	X				X	X	X					X ⁴	X ⁴
Adverse Events		X	X	X	X	X		X	X	X	X	X				X ⁵	X ⁵
SAEs/AESIs including PIMMCs/MAAEs/NOCMCs ¹³	X ¹⁴	X	X	X	X	X	X	X	X	X	X	X	X	X	X	X	X
Phone Visit ⁶			X	X					X	X							
Saliva Collection for Antibodies		X			X			X			X			X			

Abbreviations: AESI, adverse event of special interest; BP, blood pressure; d, day(s); ECG, electrocardiogram; HBsAg, hepatitis B surface antigen; HCV, hepatitis C virus; HIV, human immunodeficiency virus; MAAE, Medically Attended Adverse Event; NOCMC, New Onset Chronic Medical Condition; SAE, serious adverse event; PCR, polymerase chain reaction; PIMMC, Potentially Immune-Mediated Medical Condition; SARS-CoV-2, severe acute respiratory syndrome coronavirus 2; SCR, screening; Unsch, unscheduled

1 Includes white blood cells (WBCs), hemoglobin (Hb), platelets (PLT), alanine aminotransferase (ALT), aspartate aminotransferase (AST), alkaline phosphatase (ALP), total bilirubin, creatine kinase (CK), serum creatinine, prothrombin time (PT)/international normalized ratio (INR), and activated partial thromboplastin time (aPTT)

2 Includes WBC, Hb, PLT, ALT, AST, ALP, total bilirubin, CK, and creatinine

3 Includes SARS-CoV-2 serology (N-specific) only

4 If within 7 days after each vaccination (prime or boost dose)

5 If prior to Visit 11

Gritstone bio, Inc.
GO-009

Statistical Analysis Plan, Version 5.0
Date Issued: 09JUN2023

- 6 Can be phone, text, or e-mail contact
- 7 A nasal swab for SARS-CoV-2 should be performed within 3 days of COVID-19 symptoms and repeated after 7 days.
- 8 ECG will be performed for subjects receiving booster dose in Cohorts 1 and 2. ECG data will include heart rate and RR, PR, QT, and QRS durations.
- 9 ECG will be performed before 1st and 2nd doses of vaccination.
- 10 Cardiac biomarker assessment will be performed for subjects receiving booster dose in Cohorts 1 and 2. Cardiac biomarker assessments will include troponin T, C-reactive protein (CRP), and erythrocyte sedimentation rate (ESR).
- 11 Cardiac biomarker assessment will be performed before 1st and 2nd doses of vaccination.
- 12 In case of second dose delay (allowed -3 days/+21 days), all safety visits (Visit 08 to Visit 12) will be scheduled based on the day of the second dose (e.g., Visit 08 will occur 1 day after delayed second dose and not on Day 114). All visits will shift based on the second dose without changing the time interval between 2 consecutive visits.

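### SAP 9.1.2 has two wording inconsistencies: Table 5 prints fixed booster days for a window that is meant to follow the dose, and one duration sentence contradicts the section's own duration rule

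*SAP*

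**What the plan says.** **Occurrence window.** SAP 9.1.2 tabulates solicited adverse events for the day of each vaccination and the seven days after it. In the same sentence it refers the reader to Table 5 ("see the exact windows for each cohort in" that table). For boosted subjects in Cohorts 1 and 2, Table 5 gives the booster window as "Day 113 through Day 120". For Cohorts 3, 4 and 6 it gives Days 29 to 36. The table has no footnote on boosters given on another day.

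**Study day.** SAP 4.2, Table 2, counts study day from the "Date of Vaccination of Prime Dose", with that date as Day 1.

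**Permitted booster timing.** SAP 3.2, Table 1, heads the column for Cohorts 1 and 2 "GRT-R910 Boost 113 days (16 weeks [-3d/+21d]) after prime". The schedule in Appendix 1 (Table 7) sets the visit at Day 113 with the same tolerance. Table 8 sets the booster visit for Cohorts 3, 4 and 6 at Day 29, plus or minus 3 days.

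**Shift of visits.** Table 7, footnote 12, says that "all safety visits (Visit 08 to Visit 12) will be scheduled based on the day of the second dose". Table 8, footnote 15, says that "all safety visits (Visit 07 to Visit 12) will be scheduled based on the day of the second dose". Neither footnote mentions the Table 5 windows.

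**Duration.** One sentence in 9.1.2 reads: "Duration will be calculated as the number of days of the Solicited AE during the special window", with a reference to Table 5. The subsection on duration that follows has a different rule. It takes the longest unbroken run of days with a grade above zero, includes days reported after Day 8, and defines each run as end date minus start date plus 1. Its worked example gives 5 days.

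**The concern.** The first two primary endpoints are the occurrence of local and of systemic solicited reactions over the seven days after vaccination. The sentence that defines the count and the table it cites as exact give different booster windows whenever the booster is off its nominal day, which the plan expressly allows. A programmer who followed the table to the letter would leave out days on which reactions were being recorded and, for a late booster, would search days before the dose.

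The duration conflict has less at stake. It touches only the supporting duration summaries (outputs 14.3.1.4.3 and 14.3.1.4.4). There, though, two rules stand in one section and cannot both be applied.

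**Working it through.** **1. The plan's own figure.** In the worked example the headache is present on Days 1, 2, 5, 6, 7, 8 and 9, and absent on Days 3, 4 and 10.

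- First run: 2 − 1 + 1 = 2 days.
- Second run: 9 − 5 + 1 = 5 days.
- Longest run: 5 days, which matches the SAP.

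**2. The same data under the window sentence.** The Table 5 prime window is Days 1 to 8.

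- All symptomatic days in the window (1, 2, 5, 6, 7, 8): 6 days.
- Longest run cut off at Day 8 (Days 5 to 8): 8 − 5 + 1 = 4 days.

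Neither reading gives 5, because the SAP's answer counts Day 9, which lies outside the window.

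**3. Permitted booster days.**

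- Cohorts 1 and 2: 113 − 3 = 110 to 113 + 21 = 134, so 134 − 110 + 1 = 25 days.
- Cohorts 3, 4 and 6: 29 − 3 = 26 to 29 + 3 = 32, so 32 − 26 + 1 = 7 days.

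I take Day 113 as the target because the schedule does, and because 16 weeks is 112 days and Day 1 is the prime dose (112 + 1 = 113).

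**4. Overlap of the dose-relative window with the printed one.** For a booster on Day B the dose-relative window is B to B + 7, which is 8 days. Its overlap with a printed 8-day window starting on Day S is max(0, 8 − |B − S|).

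| Cohorts 1 and 2 (S = 113), booster day | Days of the true window covered | Printed days that precede the booster |
|---|---|---|
| 110, 111, 112 | 5, 6, 7 | 0 |
| 113 | 8 | 0 |
| 114, 115, 116, 117 | 7, 6, 5, 4 | 1, 2, 3, 4 |
| 118, 119, 120 | 3, 2, 1 | 5, 6, 7 |
| 121 to 134 | 0 | 8 |

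For Cohorts 3, 4 and 6 (S = 29) the coverage on Days 26 to 32 is 5, 6, 7, 8, 7, 6 and 5 days.

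Coverage is therefore complete on one permitted day in each schedule: 1 of 25 and 1 of 7. In Cohorts 1 and 2 it is zero on 134 − 121 + 1 = 14 of the 25 permitted days. In Cohorts 3, 4 and 6 it is never zero. These are counts of calendar days. They are not counts of subjects and not probabilities.

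**The case against.** The strongest reply is that nobody reading the whole SAP would apply Table 5 to the letter.

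- Section 9.1.2 itself describes the window relative to each dose, and the memory aid is kept after each vaccination.
- Table 5 has a column for the vaccination day, so its days can be read as nominal, as in the schedules.
- Section 9 presents booster-period safety data from the booster onward. A window lying wholly before the booster would contradict that.
- Section 4.1.1 treats the visit at which the vaccine was given as the target booster visit when visit windows overlap.
- Section 1 ties references to visits by study day to Appendix 1, where footnotes 12 and 15 move the later safety visits with the second dose.
- The planned outputs are dose-relative, for example 14.3.1.1.2: "Summary of Subjects with Solicited Adverse Events Within 8 Days After the Injection of Booster Dose by Maximum Grade".

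Most of this stands. Sections 1 and 4.1.1 and the footnotes are worded for visits rather than for analysis windows, and no text states the shift for Table 5. Even so, the intended reading is clear.

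On duration, the reply is that a titled subsection with a rule, a formula and an example plainly governs one general sentence. The revision history (Version 3.0) and Section 11 both record a change to the solicited-event calculation in 9.1.2. That makes it likely, though it is an inference, that the sentence was left over. This reply also stands. It settles which rule to keep but does not remove the contradiction.

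**Conclusion.** Both inconsistencies are real, and both are minor.

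**Window.** The definition and the table agree only for a booster on Day 113 or Day 29. The effect is nil if the dose-relative window is programmed, as the surrounding text indicates. The documents do not give actual booster days, so nothing can be said about how many subjects a literal reading would affect.

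**Duration.** The window sentence gives 6 or 4 days where the SAP's rule gives 5. Only the supporting duration summaries are affected. The occurrence endpoints are not.

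A reader might go further in two ways that the documents do not support.

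- *That booster reactogenicity will be lost for much of Cohorts 1 and 2.* The 14 of 25 figure holds only under a literal reading that the rest of the SAP contradicts, and it counts permitted days rather than people.
- *That reporting a long event as more than 8 days is a further error.* The SAP's example has 5 days inside the first 8 and 4 beyond. If consecutive, that is 9 days, so the label is true. Section 9.1.2 says only that duration will be summarised, the exact formula is already given, and clinicians collect resolution information for symptoms that persist past the window. How to display such events is a reporting preference.

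**What to change.** 1. In Table 5, state each booster window as the date of Dose 2 through the date of Dose 2 plus 7 days. Label Days 113 to 120 and Days 29 to 36 as nominal.
2. Delete the sentence that counts duration within the Table 5 window. Keep the longest-consecutive-run rule, its formula and its example.

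The cost is SAP wording only. Solicited events are already collected after each dose, and study vaccine administration is already recorded. No new data are needed, and the dosing and visit schedules do not change.
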